All participating staff and subjects will complete, in addition to the traditional paperwork and charting processes associated with standard clinical care, study documents via a password protected RedCap site on a Penn Server. These documents will be reviewed by the study coordinator on a daily basis and with the Penn PI on weekly basis. As needed reviews with the PI will occur given the incidence of an adverse event, the occurrence of treatment non-response, the incidence of patient non-adherence, or the occurrence of protocol deviations. In addition to the daily review of the study progress and problems, the study coordinator will speak on a bi-weekly basis with the Carrier Clinic coordinator and complete a checklist and notes form to document these encounters. The PI and coordinator will travel to the clinic once a month to discuss study logistics.

The study documents will include the following

- a) A subject identification form
- b) A study consent form (completed on paper w/ a signed digital copy sent to Penn staff via a secure upload method)
- c) 10 study questionnaires (e.g., the PHQ-9) completed by the patient via a RedCap site on a Penn Server according to a pre-determined schedule.
- d) 5 Tracking forms (re: patient contact, procedure details, and adverse events) completed by Carrier Clinic staff via a RedCap site on a Penn Server according to a pre-determined schedule

BACKGROUND

Electroconvulsive therapy (ECT), also referred to as “electroshock therapy,” is a psychiatric treatment where external electrical stimulation (brief-pulse currents of up to 800 millamps) is used to induce seizures. Treatments are administered, with anesthesia and muscle relaxants, 1-3 times per week over the course of several weeks, or until symptoms improve. ECT is very effective as an antidepressant, reducing depressive symptoms in approximately 50% of patients. Despite its effectiveness, it comes with significant risks. It can cause mild or severe confusion and memory loss, muscle soreness, worsening of symptoms in patients with neurologic disorders, and (as with any procedure that involves sedation), adverse effects from hypoxia. Finally, patients may also be disinclined to engage in this form of therapy owing to the social stigma associated with it and concerns about side effects. Accordingly, an alternative to ECT would be beneficial.

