TES (as administered by the Nexalin apparatus) may be a viable alternative to ECT. A prior randomized, controlled trial compared antidepressant medication with Sham TES, Placebo with Nexalin at a lower dose, and Placebo medication with Nexalin at a higher dose. All three conditions showed remission of depressed mood by the end of treatment and maintenance of remission status following 12 weeks of follow-up. Thus, the effect sizes for Nexalin treatment were comparable to antidepressant medication. It should also be noted that the Nexalin device has undergone extensive safety analysis indicating that the device is safe for its intended use. Additionally, the classification of the device places it into a nonsignificant risk (low risk device) category. A review of Phase III Pivotal Clinical Trials (with a follow up period of one year) demonstrates that Nexalin TES Therapy does not result in any significant adverse events or side effects. In fact, there was no significant difference between reported events in the placebo group and reported events in the active treatment group.

[figure not shown]
Since the direct electrical stimulation represents a similar mechanism of action to ECT, and Nexalin has not only demonstrated effectiveness in depression but also has a much better safety profile than ECT, it is possible that Nexalin treatment could be a viable, more acceptable, alternative to ECT.

STUDY GOAL

Determine whether Nexalin TES is a viable alternative to ECT in subjects who do and do not accept ECT treatment.

STUDY DESIGN

A 2x2 factor Randomized Controlled Trial with block randomization. Inpatient subjects at the Carrier Clinic who are referred for ECT will be recruited, typed regarding their acceptance of ECT, and randomized to either treatment with TES or to a Sham condition. Treatment non-responders in either condition will continue as inpatients at the Carrier Clinic until they reach acceptable levels of functioning to be discharged. For additional details, see "procedures" section of this document.

STUDY DURATION

The study will last up to 2 years. This will allow sufficient time for recruitment and completion of all subjects.

TARGET POPULATION

Patients diagnosed with major depressive disorder (MDD) who have failed antidepressant therapy with one or more medications and are referred for ECT.

INCLUSION CRITERIA

To be included in the study, patients must be:

1. In-patients at the Carrier Clinic
2. Adults over age 18 and under age 65

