3. Able to speak, read and write fluently in English, assessed by the study coordinator at Carrier Clinic
4. Screened Negative for alcohol abuse and/or dependence
5. Able to provide informed consent, assessed by the study coordinator at Carrier Clinic
6. Referred for ECT
7. Not currently taking hypnotics or be prescribed hypnotics during the Nexalin trial.
8. Not pregnant or intending to become pregnant during the study
9. Committed to completion of the study.

TOTAL SUBJECTS ENROLLED

150

VULNERABLE POPULATIONS

No vulnerable populations (as defined by socio-economic status, geography, gender, age, disability status, and other populations identified to be at-risk for health disparities) will be recruited.

RECRUITMENT & RANDOMIZATION

As noted above, patients will be directly recruited from, and receive treatment at, the Carrier Clinic. Currently, the Carrier Clinic treats approximately 1,000 unique patients who receive ECT annually, resulting in 5,200 procedures performed per year. Randomization will occur in blocks, such that for every 20 subjects enrolled, 10 will receive Nexalin and 10 will receive Sham treatment.

COMPENSATION

No financial compensation will be provided to participants for participation in the trial.

PRIMARY OUTCOMES

Percent responders and non-responders to TES treatment or Sham TES treatment (who accepted or refused ECT) as assessed with the PHQ-9 (50% reduction or a score below 10).

SECONDARY OUTCOMES

Assess whether Nexalin TES produces significantly greater gains than Nexalin Sham for

1. Depression severity (as assessed with the PHQ-9, and the QIDS)
2. Anxiety severity (as assessed with the GAD-7 and the POMS)
3. Insomnia severity (as assessed with the ISI)

Finally, we will (post hoc) assess which baseline subject characteristics differentiate between responders and non-responders.

PROCEDURES

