All patients referred for ECT and otherwise eligible for the study will be approached by the Carrier Clinic study coordinator (or his designate) and asked whether they wish to participate in the research study. All subjects will be non-responders to traditional medical approaches (patients diagnosed with MDD who have failed antidepressant therapy with one or more medications). Those that express interest will review the study protocol with the study coordinator. The study coordinator will ascertain eligibility, address any concerns, and obtain written informed consent. Following the obtention of informed consent, the subject will be scheduled (or undergo at the time) a baseline assessment. The subjects that volunteer, are eligible, and are consented for the study will be queried as to whether or not they are willing to receive ECT. This decision will be used to type each subject that consents to be in the protocol (Accept or Refuse ECT). Following randomization to one of two conditions (TES or Sham), treatment will occur twice daily (40 minutes per session, separated by 5 hours' time between the AM and PM sessions) over 3-10 days. Subjects that do not exhibit 20% attenuation of symptoms (as assessed by an AM and PM version PHQ-9) on or before 6 treatments will be designated treatment non-responders and discontinue their participation in the study while remaining as inpatients at the Carrier Clinic. Note: During the Nexalin trial, all subjects will receive standard inpatient care where the only difference in the treatment regimens are that they are receiving TES or Sham TES in place of ECT. See "Protection Against Risks" section for stopping rules during treatment for subjects who do not show sufficient treatment response.

Session Protocol. The protocol for receiving treatment will be as follows:

1. Inpatients that have enrolled in the study will receive TES or Sham TES once in the AM and once in the PM.
2. The procedure will be conducted in a semi-private room while the subject reclines in a lounge chair.
3. The two TES session will each be 40 minutes in duration, separated by 5 hours' time.
4. The TES provider will oversee the administration of the patient on-line questionnaires.
5. The TES trained provider will complete the Carrier Clinic staffforms.
6. When the TES session is complete, the subject will resume his/her regular clinic activities.

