1. Patient Enrollment Form / Candidate Screener / Enrollment Form (completed once per week per patient): This requires the staff member to profile the patient who has been approached to participate in the study and to document if they meet eligibility and have been consented.
2. Procedure Tracking form / Patient Tracking (once per session): This requires the clinician to record: the patient initials; the patient PNC ID; the date of the session; the session #; the time session was conducted; the room the session was conducted in; the identifying sticker attached to the device; the device number; whether each instrument was administered; any comments they may have about the session; whether the

patient was diagnosed with any new disorders (and if yes, please list); and whether the patient's meds have been changed (and if yes, please list).

3. Adverse Event Form (*completed as needed*): This requires the clinician to record: the patient initials; the patient PNC ID; the date of the session; description of event; information about the event onset; start date and start time of event; information about the event offset; end date and end time of event; actions taken or treatments given; the severity of the event; event symptoms; diagnostic results; information about outcomes; and if the event is on-going what additional steps are planned.

4. Clinician Information Form (*completed once*):

This requires the clinician to record: the study clinician identification number, the clinician's name, the clinician's position at the clinic, the clinician's credentials (degree), and the clinician's contact information.

5. SBJ d/c Form (*completed as needed*):

This requires that a staff member specify that a subject has been withdrawn from, or quit, the protocol and the reason for why the subject is no longer participating.

ANALYSIS PLAN

The primary analysis for the study will be an evaluation of treatment response rates using an analysis of 2x2 contingency tables, using the Cochran-Mantel-Haenszel test to assess differences in treatment response by randomization groups, stratified by patient choice. The secondary analysis will evaluate how treatment non-responders and responders differ with respect to the various demographic and clinical profile measures.

CONFIDENTIALITY

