Transcranial electric stimulation devices are classified as a Class III device. These types of devices have been used for many years and occasional adverse effects have been reported, including: headache, nausea, minor burns, increased agitation, minor rash from specific electrodes, and electrical discharge when electrodes are removed. Specifically, headaches and nausea have been noted when current levels are higher than those used in the present study. Note: the device settings for current and duration of treatment are fixed (i.e., cannot be altered by the administering clinician or technician).

Risks associated with Sham treatment:

Since the sham treatment is identical except for a lack of active electrical current, the only risks include those associated with nervousness about the procedure and skin irritation from electrodes, described above.

Risks associated with questionnaires, interviews, and physical measurements:

As the subjects in the study are psychiatric patients with relatively significant symptoms, and the assessment measures directly address some of these symptoms, it is possible that answering questions in an interview format or in a questionnaire format can arouse uncomfortable feelings or even some level of distress. Although this is very rare, it is possible.

Risks associated with loss of confidentiality:

There is a possibility that records associated with the study (particularly paper documents such as those in the study binder) will inadvertently be seen by Carrier Clinic personnel that are not affiliated with the study.

Risks associated with ECT

While there are risks associated with ECT treatment, the provision of this therapy occurs outside the proposed protocol and therefore is not a risk of the proposed study.

PROTECTION AGAINST RISKS

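### The goal is framed against ECT but every planned comparison is with sham, so the trial can answer it only in part

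*Combined protocol and SAP*

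**What the plan says.** The Study Goal section sets the question: "Determine whether Nexalin TES is a viable alternative to ECT in subjects who do and do not accept ECT treatment".

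Under Study Design, patients are "typed regarding their acceptance of ECT, and randomized to either treatment with TES or to a Sham condition". There is no ECT arm. Procedures says that during the trial the only departure from standard inpatient care is that "they are receiving TES or Sham TES in place of ECT". Potential Study Risks adds: "While there are risks associated with ECT treatment, the provision of this therapy occurs outside the proposed protocol".

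The primary outcome is the percentage of responders under TES and under sham, among those who accepted or refused ECT, "as assessed with the PHQ-9 (50% reduction or a score below 10"). The Analysis Plan tests it "using the Cochran-Mantel-Haenszel test to assess differences in treatment response by randomization groups", stratified by patient choice. The secondary outcomes ask whether TES produces greater gains than sham. The secondary analysis compares responders with non-responders.

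The one efficacy figure for ECT is in the Background: "ECT is very effective as an antidepressant, reducing depressive symptoms in approximately 50% of patients". No analysis uses it.

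**The concern.** The goal names ECT as the reference, but nothing in the design or analysis measures TES against ECT. There is no ECT arm, no historical-control analysis, no non-inferiority margin, no minimum TES response and no definition of *viable*. Accept/Refuse ECT records a stated preference and serves as a stratum; it is not an ECT treatment group.

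What is at stake is the conclusion, not the validity of the test. With the goal worded as it is, a significant TES-versus-sham result has no stated limit on what may be claimed from it. The gap matters most for patients who would accept ECT, because for them an alternative to ECT is naturally judged against ECT. The protocol itself lists delayed access to ECT, a therapy it describes as known to be effective, among the study risks.

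**Working it through.** **Step 1. Goal against comparisons.** This step needs no assumption.

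| Element | Reference | Source |
|---|---|---|
| Goal | ECT | Study Goal |
| Randomised arms | sham | Study Design, Procedures |
| Primary test | sham | Analysis Plan |
| Secondary outcomes | sham | Secondary Outcomes |
| Secondary analysis | responders v non-responders | Analysis Plan |
| ECT response of about 50% | used in no analysis | Background |

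The reference named in the goal appears in none of the comparisons.

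**Step 2. What a positive result could look like.** The plan has no figure on this point to reproduce: the total of 150 comes without alpha, power or response rates.

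Inputs from the documents: 150 subjects, and 10 TES to 10 sham in each block of 20, so about 75 per arm (150 is not a multiple of 20).

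Assumptions: two-sided 0.05, no dropout, both strata collapsed into one table, and a range of sham rates.

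Test: z = (pT − pS) / √[2·p̄(1 − p̄)/75], where p̄ is the pooled rate.

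Wilson 95% interval: [p + z²/2n ± z√(p(1 − p)/n + z²/4n²)] / (1 + z²/n), with n = 75 and z = 1.96.

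Worked case, sham 15/75 and TES 26/75:
- p̄ = 41/150 = 0.273; standard error = √(2 × 0.273 × 0.727/75) = 0.0728.
- Difference = 11/75 = 0.147; z = 2.015; p = 0.044. With 25/75, p = 0.065, so 26 is the smallest significant count.
- Wilson interval for 26/75: centre 0.354, half-width 0.105, giving 24.9% to 45.9%.

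| Sham | Smallest significant TES count | p | Wilson 95% CI for TES | Count needed with continuity correction |
|---|---|---|---|---|
| 11/75 (14.7%) | 21/75 (28.0%) | 0.046 | 19.1% to 39.0% | 22/75 |
| 15/75 (20.0%) | 26/75 (34.7%) | 0.044 | 24.9% to 45.9% | 27/75 |
| 18/75 (24.0%) | 30/75 (40.0%) | 0.036 | 29.7% to 51.3% | 31/75 |
| 26/75 (34.7%) | 38/75 (50.7%) | 0.048 | 39.6% to 61.7% | 39/75 |

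The largest TES count whose upper limit lies below 50% is 29/75 by Wilson (49.98%) and 28/75 by exact limits (29/75 gives 50.6%).

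The Analysis Plan does not say whether the test is continuity-corrected. With correction, 21 v 11 gives p = 0.073 and 26 v 15 gives p = 0.067. One more TES responder restores significance in each case, and the upper limits (40.4% for 22/75, 47.3% for 27/75) are still below 50%.

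**Step 3. Reading.** For sham response up to about 20%, the trial can be positive while its own data exclude a 50% TES response. At 24% the minimum positive result no longer excludes 50%. At about 35%, significance already requires TES above 50%.

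**The case against.** The strongest defence is that *viable* need not mean matching ECT's response rate. The Background makes the case for TES conditional on its being found efficacious, offers it for some patients only, and stresses that it avoids seizures and sedation. On that reading a less effective but more acceptable treatment can still be a viable option. For patients who refuse ECT, sham plus standard inpatient care is a reasonable comparator. This stands, and it means the sham test answers part of the goal. A reader might infer that the goal cannot be answered at all; the documents do not support that. Nor do they define *viable* in the weaker sense, and the goal expressly includes patients who would accept ECT.

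A second objection is that the 50% is a loose background statement with no instrument, threshold or time point, so it is not comparable with PHQ-9 response after 3 to 10 days. This also stands. The figure is context only and should not become a benchmark by being printed beside the TES result.

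Third, the responder percentages by arm and by accept/refuse are already the primary outcome. That is so; what is missing is the intervals and a stated limit on the conclusion.

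A reader might also infer that the trial would be reported as grounds for replacing ECT. The documents contain no such success rule. The Background's remark about clinicians and payers concerns support for TES in cases where they might not support ECT.

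**Conclusion.** The point holds as a mismatch between the goal and the design. A significant result would support efficacy over sham in inpatients referred for ECT. It would support no statement about TES relative to ECT, particularly for patients who would accept ECT. That conclusion rests on the text alone.

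The size is conditional. With 75 per arm, two-sided 0.05 and an uncorrected test, a positive trial can exclude a 50% TES response if sham response is about 20% or lower. It is tempting to say that a positive trial would generally leave TES well below ECT. The documents do not support that: they give no sham rate, the contrast is gone by about 35% sham response, and the 50% has no stated definition.

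The randomised comparison and its test are unaffected. What needs correcting is the scope of the claim.

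**What to change.** 1. Restate the goal and the permitted conclusion: whether TES is superior to sham in inpatients referred for ECT, overall and by ECT accept/refuse, with no claim of equivalence to ECT or of replacing it.

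2. Pre-specify the TES and sham response rates and their difference with 95% CIs, overall and within each stratum. The Cochran-Mantel-Haenszel test gives one common result, so the stratum figures should be read as estimates. They will be imprecise. At assumed rates of 35% v 20% and an even accept/refuse split (37.5 per arm per stratum), the half-width of the difference is 1.96 × √(0.2275/37.5 + 0.16/37.5) = 0.20, against 0.14 overall with 75 per arm.

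3. Optional, if consent allows: for every randomised subject, record at hospital discharge whether ECT was given later in the same admission, and report it descriptively by arm and stratum. The SBJ d/c Form will not serve. It covers only subjects who are withdrawn or quit, so it misses completers, and it is filled in at study exit, before any later ECT.

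Cost: items 1 and 2 need rewording and a few interval estimates, with no new patients or visits; the downside is a narrower headline claim. Item 3 needs a small amount of record abstraction after study exit.

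Keeping the ECT framing would cost far more. A non-inferiority comparison with a concurrent ECT arm, assuming 50% response in both arms, one-sided 0.025, 80% power and a 15-point margin (the documents give none), needs 2 × 0.25 × (1.960 + 0.842)²/0.15² ≈ 175 per arm. The range is 393 to 99 per arm for margins of 10 to 20 points.

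### Allocation is blocked over all subjects enrolled and not within the Accept and Refuse ECT types that the analysis stratifies on, so balance within each type is left to chance (minor, cheap to fix)

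*Combined protocol and SAP*

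**What the plan says.** STUDY DESIGN describes "A 2x2 factor Randomized Controlled Trial with block randomization". It gives the order of events: inpatients referred for ECT are "recruited, typed regarding their acceptance of ECT, and randomized to either treatment with TES or to a Sham condition". PROCEDURES agrees: every consented subject is asked about willingness to have ECT, and the answer fixes the subject's type.

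The type is then used throughout. STUDY GOAL reads "Determine whether Nexalin TES is a viable alternative to ECT in subjects who do and do not accept ECT treatment". PRIMARY OUTCOMES defines response by arm among those who accepted or refused ECT. ANALYSIS PLAN uses a CMH test to "assess differences in treatment response by randomization groups, stratified by patient choice".

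The allocation rule is in RECRUITMENT & RANDOMIZATION: "Randomization will occur in blocks, such that for every 20 subjects enrolled, 10 will receive Nexalin and 10 will receive Sham treatment". No section forms blocks within type. No section gives an expected number, minimum or quota for either type.

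**The concern.** ECT acceptance is one of the two factors of the design, and it is known before allocation. The analysis conditions on it, but the allocation rule as written ignores it. Equal arms in each run of 20 enrolled subjects do not imply equal arms among refusers or among acceptors.

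What is at stake is the TES versus Sham comparison within each type, above all the smaller one. An uneven split there widens the interval around the difference in response rates. It also lets the mix of acceptors and refusers differ between arms, which would matter to anyone reading response rates by arm without regard to type. Neither can be repaired after enrolment.

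**Working it through.** **Plan's own figure.** The plan states 150 subjects but no alpha, power or response rates, so 150 cannot be reproduced. For orientation only: 75 per arm, two-sided 0.05 and 30% versus 50% response give about 71% power.

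**Inputs from the documents.** N = 150; blocks of 20 (10:10) over all enrolled; typing before randomisation; CMH stratified by type.

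**Assumed input.** Size m of the smaller type. It is not stated, so a range is shown, with these subjects scattered at random through the enrolment order.

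**Step 1: spread of the split.** Let k be the number of the m subjects who receive TES. With 75 of 150 on TES, k is hypergeometric, with variance m × 1/4 × (150 − m)/149.
- m = 15: 15 × 0.25 × 135/149 = 3.40, SD 1.84
- m = 30: 30 × 0.25 × 120/149 = 6.04, SD 2.46
- m = 45: 45 × 0.25 × 105/149 = 7.93, SD 2.82

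Simulation of the block rule (40,000 runs per m) gives SDs of 1.86, 2.47 and 2.82.

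**Step 2: loss of precision.** Relative to an even split, and with equal response variance in the arms, the variance of the within-type difference is multiplied by R = (1/k + 1/(m − k)) / (4/m).
- 5:10 gives (0.200 + 0.100)/(4/15) = 1.125. The standard error rises by √1.125 − 1 = 6%. A 10:20 split gives the same ratio.
- 4:11 gives (0.250 + 0.091)/(4/15) = 1.28. The standard error rises by 13%.

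**Step 3: how often.**

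| Smaller type, m | Share of 150 | 95% range on TES | P(60:40 or worse) | P(2:1 or worse) | Mean R | 95th percentile of R |
|---|---|---|---|---|---|---|
| 15 | 10% | 4–11 | 59% | 28% | 1.08 | 1.28 |
| 30 | 20% | 10–20 | 31% | 7% | 1.03 | 1.125 |
| 45 | 30% | 17–28 | about 16% | 1% | 1.02 | 1.06 |

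The exact hypergeometric calculation, allowing for the half-filled eighth block, agrees: 27.7%, 6.6% and 1.3% for 2:1 or worse.

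**Step 4: effect on the primary test.** CMH without continuity correction, 20,000 runs per setting. Smaller type of 15, 30, 45 or 75; Sham response 30% in the larger type and 15%, 30% or 45% in the smaller.
- Type I error under the overall list: 4.7% to 5.2%.
- Power for a 20-point gain, with 30% Sham response in both types: about 71%, against about 72% with evenly split types. The largest loss in any setting is 72.3 − 70.8 = 1.5 points (m = 30). The Monte Carlo standard error of each power is about 0.3 points.

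**Step 5: effect within a type.** Power for 30% versus 60% response is 37% at 15:15 and 35% at 10:20. With 15 subjects it is about 20% at either 8:7 or 5:10.

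**Step 6: with separate lists.** Keeping blocks of 20 within each type, the chance of 2:1 or worse is 18% at m = 10 (there, 7:3 or worse), 3% at m = 15 and 0% at m = 20 or more. With blocks of 4 it is 0% at every m tested. In general the final difference between arms within a type cannot exceed half a block. With blocks of at most 6 it is at most 3, whereas a 2:1 split needs a difference of at least m/3, which exceeds 3 once m is 10 or more.

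**The case against.** The strongest reply is that this hardly affects what the plan tests. CMH conditions on the number per arm within each type, so it is valid whatever the split. No separate test within type is planned, so by-type results are descriptive. Where an uneven split is likely, the type is so small that perfect balance would not rescue the comparison (step 5). Where the type is large enough to inform, an uneven split is rare. All of this stands, and it sets the size of the point.

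Two further replies stand in part. The plan does not rule out separate lists in words. A single list is the plain reading of a rule that counts every 20 enrolled, but the sponsor may intend otherwise; the same sentence would settle it. Shorter blocks also carry a cost: staff record the device number and its sticker at each session, and active current may cause tingling or burning while sham passes none. If allocations are guessed, short blocks make the next one easier to predict.

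A reader might infer that the Refuse group must be small, because the clinic's volume of about 1,000 patients a year counts those who receive ECT. That figure does not show how many referred patients refuse. BACKGROUND says that patients may be reluctant to have ECT, and refusers might enrol readily. A reader might also object that 150 is not a multiple of 20. The half-filled last block moves each arm's total by about one subject (SD about 1.1) and is trivial.

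**Conclusion.** The gap is real and minor. As written, allocation is not stratified by the factor that defines the design and stratifies the primary test. How often that yields an uneven type depends on a size the documents do not give: a 2:1 or worse split has a chance of about 28% with 15 subjects in the smaller type, 7% with 30 and 1% with 45. Even a 2:1 split raises the standard error of the within-type difference by only about 6%.

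A reader might infer that the primary analysis is biased or seriously weakened, or that a type will be badly split. The documents do not support either. The planned test adjusts for type, keeps its error rate and loses at most about 1.5 points of power under the response rates assumed above. The benefit of a change lies in the by-type response rates and in making allocation match the analysis. The case for it is that it costs very little and must be made before enrolment.

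**What to change.** In RECRUITMENT & RANDOMIZATION, replace the blocking sentence with wording such as: *Subjects are typed Accept or Refuse ECT before allocation and are randomised 1:1 within each type from separate block lists, with randomly varied block sizes shorter than 20 that are concealed from treating and recruiting staff.* Hold the actual block sizes in a restricted randomisation document. State the expected number of subjects of each type alongside.

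The separate lists are the main gain. Shorter blocks matter only if a type may have fewer than about 20 subjects (step 6).

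Cost: one extra list and one sentence, with no added subjects, visits or staff. The drawback is slightly more predictable allocation, which concealed, varied block sizes limit. The CMH analysis needs no change.
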